#### **9.2.6 Influenza patient reported outcomes**

The FluPRO is a 32-question instrument that assesses occurrence and severity of influenza symptoms over the last 24 hours. The instrument questions, and the conversion from text to numeric values, are presented in Appendix 16.3.1. A description of the calculation of domain, component, and total symptom scores is presented in Appendix 16.3.2.

The FluPRO data are collected for subjects able to complete the instrument at Day 1(Baseline), then every day through Day 14. These data will be summarized at each visit with counts and

January 17, 2019

percentages by treatment group, including a combined low-dose and high-dose VIS410 group. Analyses of FluPRO variables will be conducted only on the subset of the MITT population who had a baseline FluPRO Questionnaire assessment.

The number and percentage of subjects with and without symptoms for each domain, component and total symptom scores will be summarized overall and for each day. In these analyses, a subject mean score >1 will be analyzed as having symptoms and a mean score less than or equal to 1 will be analyzed as not having symptoms. The number and percentage of subjects who were not able to complete the assessment at each visit will be summarized by treatment group.

Descriptive statistics (n, mean, SD, median, minimum, and maximum) will be used to compare the duration of symptoms of influenza-like illness in the subset of subjects able to complete the FluPRO Questionnaire at baseline and post-dose by treatment group. The duration of an individual symptom will be defined as the earliest visit day from 2 consecutive answers of 'no symptom' defined as 'Not at all' or 'A little bit' for questions 1 – 27; 'Never' or 'Rarely' for questions 28 and 30 and '0 times' or '1 time' for questions 31 and 32. The duration of total symptom score, domain symptom scores, or component symptom scores will be defined as the earliest visit day from 2 consecutive means  $\leq 1.0$ . A missing value cannot contribute to the 2 consecutive 'no symptom' days. If a subject has 'no symptoms' at baseline for a question, total symptom score, domain symptom scores, and component symptom scores, duration will be defined as zero for that question. If a subject has not had 2 consecutive 'no symptom' responses or 2 consecutive means  $\leq 1.0$  by the Day 14 FluPRO survey, the subject's data will be listed as ">14" and summarized as 14 days. Treatment group comparisons will be based on Analysis of Variance (ANOVA) using rank-transformed values.

Kaplan-Meier methods will also be used to calculate the median time, 25th percentile, and 75th percentile time to resolution. P-values for each VIS410 dose versus placebo, VIS410 total versus placebo and for VIS410 4000 mg versus 2000 mg will be presented based on log-rank tests. Resolution for the total symptom score is defined as a mean score  $\leq 1.0$  and all 6 domain scores are  $\leq 1.0$ . Resolution for the 6 domain scores and the 3 component scores is defined as a mean score  $\leq 1.0$ .

The total symptom score, the 6 domain symptom scores, and the 3 component symptom scores will be summarized by treatment group at each visit (including change from baseline and percent change from baseline to each visit), with n, mean, SD, median, minimum, and maximum by treatment group, including a combined low-dose and high-dose VIS410 group. The differences for each VIS410 dose versus placebo, VIS410 total versus placebo and for VIS410 4000 mg versus 2000 mg will be tested using ANOVA based on ranks. The maximum severity of symptoms overall and on each day will be summarized for the domain, component, and total symptom scores.

Area under the curve (AUC) for the total symptom score, 6 domain symptom scores, and 3 component symptom scores will be calculated using the linear trapezoidal rule, i.e.  $AUC_{t_i, -t_{i+1}} = 1/2 * (S_i + S_{i+1}) * (t_{i+1} - t_i)$  where  $S_i$  is the total symptom score at time point  $t_i$ . All time points from pre-dose to Day 14 will be considered.

January 17, 2019

Additional exploratory analysis, including but not limited to evaluation of sums instead of means of symptom scores, may be performed for the total symptom score, 6 domain symptom scores, and 3 component symptom scores.

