## 16.3 FluPRO Questionnaire

### 16.3.1 Individual Questions

The FluPRO questionnaire collects information on influenza symptoms over the last 24 hours. These questions have possible answers of Not at all, A little bit, Somewhat, Quite a bit, or Very much. 'Not at all' is considered 'no symptom'.

1. Runny or dripping nose
2. Congested or stuffy nose
3. Sinus pressure
4. Scratchy or itchy throat
5. Sore or painful throat
6. Difficulty swallowing
7. Teary or watery eyes
8. Sore or painful eyes
9. Eyes sensitive to light
10. Trouble breathing
11. Chest congestion
12. Chest tightness
13. Dry or hacking cough
14. Wet or loose cough
15. Felt nauseous
16. Stomach ache
17. Felt dizzy
18. Head congestion
19. Headache
20. Lack of appetite
21. Sleeping more than usual
22. Body aches or pains
23. Weak or tired
24. Chills or shivering
25. Felt cold
26. Felt hot
27. Sweating

For numeric summaries, Not at all = 0; A little bit=1; Somewhat=2; Quite a bit=3; Very much=4.

These questions have possible answers of Never, Rarely, Sometimes, Often, Always. 'Never' is considered 'no symptom':

28. Sneezing
29. Coughing
30. Coughed up mucus or phlegm

For numeric summaries, Never = 0; Rarely = 1; Sometimes =2; Often = 3; Always = 4.

January 17, 2019

These questions have possible answers of 0 times, 1 time, 2 times, 3 times, 4 or more times. '0 times' is considered 'no symptom':

31. How many times did you vomit?
32. How many times did you have diarrhea?

For numeric summaries 0 times = 0; 1 time = 1; 2 times = 2; 3 times = 3; 4 or more times = 4.

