### **16.3.2 Calculation of Domain, Component and Total Symptom Scores**

The domain, component, and total symptom scores for an individual will be calculated as the mean of the questions that are non-missing. The minimum data requirement for calculating each of the domain symptom scores is: nose 3 of 4 items, throat 2 of 3 items, eyes 2 of 3 items, chest/respiratory 5 of 7 items, gastrointestinal 3 of 4 items, and body/systemic 8 of 11 items. Total symptom scores will only be calculated if the conditions of missing data for all domains are met.

The domain symptom scores are defined as:

- Nose: Running or dripping nose, congested or stuffy nose, sneezing, sinus pressure
- Throat: Scratchy or itchy throat, sore or painful throat, difficulty swallowing
- Eyes: Teary or watery eyes, sore or pain eyes, eyes sensitive to light
- Chest/Respiratory: Trouble breathing, chest congestion, chest tightness, dry or hacking cough, wet or loose cough, coughing, coughed up mucus or phlegm
- Gastrointestinal: Nausea, stomach ache, vomiting, diarrhea
- Body/Systemic: Felt dizzy, head congestion, headache, lack of appetite, sleeping more than usual, body aches or pains, weak or tired, chills or shivering, felt cold, felt hot, sweating

The component symptom scores are defined as:

- Upper Respiratory Tract: Runny or dripping nose, congested or stuffy nose, scratchy or itchy throat, sore or painful throat, sneezing, difficulty swallowing, teary or watery eyes, sore or painful eyes, eyes sensitive to light,
- Lower Respiratory Tract: Trouble breathing, chest congestion, chest tightness, coughing, dry or hacking cough, wet or loose cough, coughed up mucus or phlegm
- Generalized: Nausea, vomiting, diarrhea, stomach ache, felt dizzy, sinus pressure, head congestion, headache, lack of appetite, sleeping more than usual, body aches or pains, weak or tired, chills or shivering, felt cold, felt hot, sweating

January 17, 2019

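### For the FluPRO total score, the with/without-symptom summary and the duration rule omit the six-domain condition that SAP 9.2.6 requires for Kaplan-Meier resolution, so one subject can have contradictory status on one score

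*SAP*

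**What the plan says.** SAP 9.2.6 describes FluPRO as a 32-item instrument. Items are scored 0 to 4 (SAP 16.3.1: "For numeric summaries, Not at all = 0; A little bit=1; Somewhat=2; Quite a bit=3; Very much=4", with the same 0 to 4 range for the frequency and count items). Under SAP 16.3.2, "The domain, component, and total symptom scores for an individual will be calculated as the mean of the questions that are non-missing". The total is therefore an unweighted item mean.

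SAP 9.2.6 then applies these rules to the total score:

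- **With/without-symptom summary.** Subjects are counted as with or without symptoms separately on every domain, component and total score, both overall and by day. A mean above 1 counts as having symptoms, and "a mean score less than or equal to 1 will be analyzed as not having symptoms". The total carries no further condition.
- **Duration, compared by ANOVA on ranks.** Duration "will be defined as the earliest visit day from 2 consecutive means" at or below 1.0. It is set to zero when there are no symptoms at baseline, and the total score is among the scores named. A subject who has not met the rule by Day 14 is summarized as 14 days.
- **Kaplan-Meier time to resolution, compared by log-rank test.** "Resolution for the total symptom score is defined as a mean score" at or below 1.0, with every one of the six domain scores also at or below 1.0. This is the only place where the domain condition appears.

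For domain and component scores the cut-off is 1.0 throughout, so the discrepancy concerns the total score only.

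**The concern.** The SAP adds the domain condition once, which implies that a low total mean alone was not thought enough to call a subject resolved. It leaves the condition out of the other two uses of the same score and gives no reason. SAP 16.1, which lists changes from the protocol analyses, does not mention it.

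A mean over 32 items can stay at or below 1 while one domain is severe. The proportion table (14.2.6.2.1), the duration table (14.2.6.3.1) and the time-to-resolution table (14.2.6.6.1) could then give different answers for the same subject on the same score.

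Duration of symptoms on FluPRO is a listed secondary endpoint (protocol 3.2, SAP 3.2), and Kaplan-Meier time to alleviation is a listed secondary objective (protocol 2.2, SAP 2.4.2). The trial's stated purpose is to compare the strength of evidence across endpoints when choosing them for Phase 3 (protocol 10.1, SAP 2.2). If duration and time to resolution end on different definitions, part of any difference in their evidence comes from the definitions.

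**Working it through.** The documents give no figure on this point to reproduce. The check is direct arithmetic.

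**Inputs.** Domain item counts (SAP 16.3.2): nose 4, throat 3, eyes 3, chest/respiratory 7, gastrointestinal 4, body/systemic 11. Sum: 4 + 3 + 3 + 7 + 4 + 11 = 32. Components: 9 + 7 + 16 = 32. Both agree with the stated 32 questions. The maximum item score is 4. The cut-off is 1.

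**Formula.** Total = sum of item scores / number of items answered.

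**Severe chest pattern, complete data.** All 7 chest items at 4, the other 25 at 0:

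- Total = 7 × 4 / 32 = 28/32 = 0.875.
- Chest domain = 28/7 = 4.0. The lower respiratory component has the same 7 items, so it is also 4.0.
- Room left for the other 25 items: 32 − 28 = 4 points. At 4 points the total is 32/32 = 1.0, still without symptoms. At 5 points it is 33/32 = 1.03, with symptoms.

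| Output for the total score | Condition | Status of this subject |
|---|---|---|
| With/without summary | total ≤ 1 | without symptoms |
| Duration | total ≤ 1.0 on 2 consecutive days; zero if without symptoms at baseline | zero if the pattern is present at baseline |
| Kaplan-Meier time to resolution | total ≤ 1.0 and all 6 domains ≤ 1.0 | unresolved |

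The zero in the second row assumes that no symptoms at baseline on the total score means a mean of 1 or less. That is the only definition SAP 9.2.6 gives for a score. If this subject's chest domain stayed above 1.0 through Day 14, the current rule would give a duration of 0 days. A rule with the domain condition would give the capped value of 14.

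**Milder pattern.** All 7 chest items at 2 and 18 other items at 1: (14 + 18)/32 = 1.0. The total says without symptoms. The chest domain is 2.0, so Kaplan-Meier says unresolved.

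**Other domains.** With one domain wholly at 4 and all else at 0, the total is: nose 16/32 = 0.50; throat 12/32 = 0.375; eyes 12/32 = 0.375; chest 0.875; gastrointestinal 16/32 = 0.50; body/systemic 44/32 = 1.375. Only body/systemic crosses the cut-off by itself.

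**Missing items.** The severe chest pattern stays at or below 1 while at least 28 items are answered (28/28 = 1.0). With all 7 chest items answered and every other domain at its minimum, 3 + 2 + 2 + 7 + 3 + 8 = 25 items are answered and the total is 28/25 = 1.12, with symptoms.

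**The case against.** A reader might infer that anyone with maximal chest symptoms is reported as symptom-free. The documents do not support that, for two reasons. The summary classifies each domain, component and total score separately, so the chest domain and lower respiratory rows of the same table count this subject as having symptoms. And the 0.875 to 1.0 range needs the other 25 items to sum to 4 points or fewer with complete data; 5 points, or enough missing items, reverses the classification. The milder pattern shows that the contradiction does not need an extreme case, but it does not show how common it is.

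A reader might also infer that symptom-free counts are materially inflated because disease in these patients sits mainly in the chest. The oxygen requirement makes this plausible, but neither document says so. Inclusion criterion 3 lists many systemic symptoms, and 11 of the 32 items are body/systemic. Adding a condition can only lower the without-symptom count, so the direction is certain. The amount is not. All arms share the same rule, and no bias in the treatment comparison has been shown.

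The stronger defence is that the protocol names Kaplan-Meier for time to alleviation, and that analysis already has the safeguard. Daily scores, maximum severity and AUC by domain do not depend on the cut-off. SAP 9.2.6 attaches no test to the with/without summary. The study is exploratory, with unadjusted p-values given for information. All of this stands and limits the importance of the point. It does not remove the contradiction, because duration is itself a listed endpoint and is tested.

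It is also fair that duration and resolution are different measures: one needs two consecutive days and the other, as written, does not. That explains a difference in timing. It does not explain why the domain condition applies to only one of them.

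**Conclusion.** The point holds for the total score only. SAP 9.2.6 as written can class a subject as without symptoms, with a duration of zero, on a score for which the Kaplan-Meier time-to-resolution analysis calls the same subject unresolved. In the severe chest case the total is 0.875 to 1.0 against a chest domain of 4.0. In the milder case it is 1.0 against 2.0.

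This rests on complete questionnaires, on the unweighted item mean in SAP 16.3.2, and on reading no symptoms at baseline as a mean of 1 or less. The domain condition belongs to time to resolution (Table 14.2.6.6.1). The separate Kaplan-Meier table of duration (14.2.6.7.1) appears to follow the duration rule and so to lack it.

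Frequency and any between-arm effect cannot be determined from the documents. The outputs are secondary FluPRO analyses in MITT subjects with a baseline questionnaire, and the Day 7 ordinal endpoint is untouched. The change should be made, but nothing about the primary conclusion depends on it.

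**What to change.** For the total score, use the SAP's own resolution condition (total mean ≤ 1.0 and all six domain scores ≤ 1.0) in three places in SAP 9.2.6: the with/without-symptom summary, the duration rule and the baseline zero-duration rule. Keep the two-consecutive-day requirement for duration, and say that this is the one remaining difference from resolution. State which rule Table 14.2.6.7.1 follows.

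No new data are needed. SAP 16.3.2 calculates the total only when every domain meets its minimum, so all six domain scores exist whenever the total does. The work is SAP wording and matching programming, best done before unblinding. The cost is that fewer subjects are classed as without symptoms on the total score and durations are longer, with more values possibly at the 14-day cap.

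If the sponsor prefers the present cut-off, the minimum is to label the row as total mean of 1 or less, instead of as not having symptoms, and to explain why it differs from resolution.

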Three subjects in Group 1 and 3 subjects in Group 3 experienced transient loose stool that resolved spontaneously. Only 1 of 4 subjects in Group 2 pretreated with diphenhydramine and ibuprofen experienced mild and transient loose stools. Based on these results, it was determined that the regimen of diphenhydramine plus ibuprofen resulted in the best tolerability profile, and this pretreatment regimen was further assessed in 4 subjects at the 4600-mg dose of VIS410 following viral challenge. Overall, 4600 mg of VIS410 following pretreatment was generally well tolerated. None of the 4 subjects reported cramping or any other symptoms associated with severe infusion reactions. Mild and transient loose stools were observed in 3 of the subjects; one event was considered unrelated to study drug. A fourth subject had a transient episode of nausea and vomiting about 8.3 hours after the start of infusion. All events were considered resolved within 24 hours of onset.

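### FluPRO duration is set to zero, the best rank, for anything symptom-free at the pre-infusion baseline, so the duration analysis cannot see symptoms that start after infusion

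*SAP*

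**What the plan says.** FluPRO is completed at baseline on Day 1 and daily to Day 14. SAP 4.1 defines baseline as the last value before study drug. Under SAP 9.2.6, the duration of an item is the first day of two consecutive no-symptom answers. For a total, domain or component score it is the first day of two consecutive means of 1.0 or less. Subjects who never reach this are summarized as 14 days.

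One sentence then overrides this for anyone without symptoms "at baseline for a question, total symptom score, domain symptom scores, and component symptom scores". It ends "and component symptom scores, duration will be defined as zero for that question", and it contains no condition on later days. For testing, "Treatment group comparisons will be based on Analysis of Variance (ANOVA) using rank-transformed values".

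The SAP gives two item cut-offs. For vomiting and diarrhea, 9.2.6 treats "0 times' or '1 time' for questions 31 and 32" as no symptom, and it likewise accepts 'A little bit' and 'Rarely' for other items. Appendix 16.3.1 is stricter: "Not at all' is considered 'no symptom" and "0 times' is considered 'no symptom". The frequency cut-off in 9.2.6 names questions 28 and 30 but omits question 29 (coughing).

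Appendix 16.3.2 defines one domain as "Gastrointestinal: Nausea, stomach ache, vomiting, diarrhea".

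**The concern.** Zero is the lowest possible duration and takes the best rank. The rule gives it both to a subject who never has the symptom and to one who develops it after infusion. These are opposite outcomes for a treatment comparison.

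The loss need not be even across arms. Diarrhea or loose stool, nausea, vomiting and abdominal cramping are on the VIS410 list of adverse events of special interest (Protocol 9.1.3). Protocol 1.3.3.1 reports GI events more often on VIS410 than on placebo. Protocol 1.3.2.2 places most of those in the first challenge cohort during infusion or within 30 minutes of its end. FluPRO asks about the past 24 hours, so such an event would normally first appear in the Day 2 answers, after baseline status has already fixed the duration at zero.

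FluPRO duration is part of a secondary endpoint (SAP 3.2), and the trial's tests are meant to guide the choice of Phase 3 endpoints (SAP 2.2). For items often absent at entry, most ranks would be tied zeros that say nothing about treatment.

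**Working it through.** The plan gives no figure for this rule, so there is none to reproduce.

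**1. Item scores.** The 9.2.6 rule applied to the diarrhea item, with 0 or 1 episode counted as no symptom:

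| Course over Days 1-14 | SAP rule | Two-day rule without the zero sentence |
|---|---|---|
| Never any | 0 | 1 |
| None at baseline, 4 or more times on Day 2 only | 0 | 3 |
| None at baseline, 4 or more times on Days 2-4 | 0 | 5 |
| None at baseline, 4 or more times on Days 2-14 | 0 | 14 |
| Twice at baseline, clear from Day 2 | 2 | 2 |

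The Day 2 case is closest to the protocol's experience, where GI events mostly resolved within about 12 to 24 hours (Protocol 1.3.1.2 and 1.3.2.2). The Days 2-14 row only shows how far the rule reaches.

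**2. GI domain.** The score is a mean of four items, each 0 to 4. With all four answered, diarrhea at its maximum and the others at zero give 4/4 = 1.0, which counts as no symptoms. Diarrhea alone therefore cannot make the domain symptomatic, with or without the zero rule. Several items raised together can: (3 + 3 + 4 + 4)/4 = 3.5 on Day 2, still scored zero if the baseline mean was 1.0 or less.

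**3. Number affected.** The share free of GI symptoms at baseline is not given; 50% to 90% is assumed. The pretreated 2300 mg rates in Protocol 1.3.3.1 are 1/11 = 9.1% and 2/12 = 16.7%. Per arm, number = 40 x share free at baseline x event rate:

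- 40 x 0.5 x 0.091 = 1.8; 40 x 0.9 x 0.091 = 3.3
- 40 x 0.5 x 0.167 = 3.3; 40 x 0.9 x 0.167 = 6.0

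This is about 2 to 6, and it is an upper bound at these rates. The two subjects behind 16.7% each had a mild loose-stool episode, one also with mild nausea. Episodes scored '1 time' or 'A little bit' count as no symptom under 9.2.6 anyway. As a sensitivity check, Protocol 1.3.3.1 describes three of 12 pretreated subjects at 3800 mg with GI symptoms. The same formula gives 40 x 0.5 x 0.25 = 5 to 40 x 0.9 x 0.25 = 9, with the same caveat.

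**4. Effect on the test.** A simulation compared 80 pooled VIS410 with 40 placebo subjects on ranks (2000 runs, two-sided 0.05). All rates are assumptions: 10% or 30% symptomatic at baseline with the same clearing in both arms; new onset in 10%, 25% or 50% on VIS410 and 2% on placebo; new episodes scored 3 or 4 days.

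| Symptomatic at baseline | New onset, VIS410 | SAP rule: mean difference (days), rejection | New onset counted: mean difference (days), rejection |
|---|---|---|---|
| 10% | 10% | 0.01, 3.8% | 0.26, 15.9% |
| 10% | 25% | 0.00, 4.5% | 0.71, 71.2% |
| 10% | 50% | -0.01, 4.9% | 1.51, 99.7% |
| 30% | 10% | 0.00, 5.0% | 0.20, 8.6% |
| 30% | 25% | -0.01, 4.8% | 0.56, 35.7% |
| 30% | 50% | 0.00, 5.3% | 1.18, 89.7% |

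Under the SAP rule the longer durations on VIS410 disappear, but no spurious difference in favour of VIS410 appears. The 10% rows are nearest the pretreated 2300 mg rates.

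**The case against.** The strongest reply is that the loss is confined to one derived variable. SAP 9.2.6 also plans by-visit total, domain and component scores with change from baseline and rank tests, maximum severity, daily proportions with symptoms, and AUC over all days. The listed adverse events of special interest are compared by arm (SAP 12.1). The trial is unpowered and its p-values are informational (SAP 2.2, 4.1). All of this stands and limits the harm. It does not make the duration value right, and for individual items duration is the only between-arm test that 9.2.6 specifies. Adverse-event capture is likely but not certain: Protocol 9.1.2 keeps influenza symptoms out of adverse-event reporting, and inclusion criterion 3 names diarrhea, nausea and vomiting among those symptoms.

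A second reply is that duration is meant to describe the presenting illness only. Subjects without the symptom at entry should then be left out, not given the best rank.

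A third is that the remedy below also takes new onset out of the tested comparison. That is true. It makes the comparison mean what its name says and puts onset in plain view, but it does not add a test for onset.

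A reader might also infer that symptoms appearing from Day 3 are lost because of the zero rule. They are not: with Days 1 and 2 clear, the two-day definition already fixes duration at Day 1.

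**Conclusion.** The concern holds for the FluPRO duration analysis. As written, the rule gives post-infusion onset the best possible value and fills the ranks with uninformative zeros. At the pretreated 2300 mg rates, and assuming 50-90% free of GI symptoms at baseline, at most about 2 to 6 subjects per 40-subject arm would have a new GI episode entered as zero. The true number cannot be determined from the documents. The GI domain is affected only when several of its items rise together.

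Three stronger readings are not supported.

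- A reader might infer that the rule manufactures a VIS410 benefit. It masks worsening; in the simulation the difference stays near zero.
- A reader might infer that the trial as a whole hides GI harm. The other FluPRO and safety outputs would still show it.
- A reader might apply the 4600 mg experience, where "Mild and transient loose stools were observed in 3 of the subjects" out of four, and obtain 40 x 0.5 x 0.75 = 15 to 40 x 0.9 x 0.75 = 27 per arm. That dose is not in this trial, one of the events was judged unrelated, and Protocol 1.5 reports two of four, so those figures should not be used.

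Separately, the item cut-offs in 9.2.6 and Appendix 16.3.1 conflict, and question 29 has none in the duration rule. This matters here because the cut-off decides who receives zero.

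**What to change.** Replace the zero sentence in SAP 9.2.6 with a rule to this effect: duration for a question, domain, component or total score is analysed in subjects symptomatic for it at baseline. For subjects without it at baseline, report by treatment group the number and percentage with post-baseline onset, and the days from the first symptomatic day to the first of two consecutive no-symptom days.

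State one item-level definition of no symptom, use it in both 9.2.6 and Appendix 16.3.1, and include question 29.

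The cost is SAP wording and one additional table from data already collected. The downside is fewer subjects in each duration analysis, although those removed would have contributed only zeros.
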